1.2 Intended aim(s)

To compare the risk of stroke or systemic embolism in nonvalvular atrial fibrillation (AF) patients at increased risk for stroke with rivaroxaban versus warfarin use.

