5.3 Flowchart of the study cohort assembly

For rivaroxaban vs. warfarin

	Optum		Truven		Medicare	
	Less Excluded Patients	Remaining Patients	Less Excluded Patients	Remaining Patients	Less Excluded Patients	Remaining Patients
All patients		75,894,642		200,203,908		6,886,908
Did not meet cohort entry criteria	-74,960,282	934,360	-199,073,812	1,130,096	-2,028,461	4,858,447
Excluded due to insufficient enrollment	-92,301	842,059	-95,091	1,035,005	-1,551,114	3,307,333

Excluded due to prior use of referent	-482,398	359,661	-622,538	412,467	-2,080,069	1,227,264
Excluded due to prior use of exposure	-205,565	154,096	-204,425	208,042	-660,796	566,468
Excluded because patient qualified in >1 exposure category	-7	154,089	-26	208,016	-81	566,387
Excluded based on Age	-624	153,465	0	208,016	-155	566,232
Excluded based on Gender	0	153,465	0	208,016	0	566,232
Excluded based on Inclusion #1 - Age >=18	-86	153,379	-264	207,752	-65	566,167
Excluded based on Inclusion #2 & 3 - Atrial fibrillation	-83,438	69,941	-129,172	78,580	-348,521	217,646
Excluded based on Inclusion #4	-13,297	56,644	-16,046	62,534	-36,136	181,510
Excluded based on Exclusion #1a - Mitral stenosis	-275	56,369	-154	62,380	-399	181,111
Excluded based on Exclusion #1b - Prosthetic heart valve	-1,238	55,131	-789	61,591	-3,016	178,095
Excluded based on Exclusion #1e - atrial myxoma or left ventricular thrombus	-158	54,973	-35	61,556	-234	177,861
Excluded based on Exclusion #1f - Active infective endocarditis	-279	54,694	-138	61,418	-401	177,460
Excluded based on Exclusion #2a - Active bleeding or bleeding history	-3,413	51,281	-2,716	58,702	-8,256	169,204
Excluded based on Exclusion #2b.1 - Major Surgery	-1,564	49,717	-1,561	57,141	-6,484	162,720
Excluded based on Exclusion #2b.2 - Bleeding diathesis	-1,235	48,482	-885	56,256	-3,832	158,888
Excluded based on Exclusion #2b.3 - Intracranial neoplasm, AV malformation, cerebral aneurysm	-259	48,223	-283	55,973	-422	158,466
Excluded based on Exclusion #2d - Thrombocytopenia	0	48,223	0	55,973	0	158,466
Excluded based on Exclusion #2e - Uncontrolled hypertension	-47	48,176	-105	55,868	-300	158,166
Excluded based on Exclusion #3a.1 - stroke plus disabling stroke effects	-257	47,919	-152	55,716	-847	157,319
Excluded based on Exclusion # 3a.2 - stroke	-103	47,816	-88	55,628	-642	156,677
Excluded based on Exclusion #3b - TIA	-17	47,799	-25	55,603	-123	156,554
Excluded based on Exclusion #3c - DVT & PE	-1,095	46,704	-853	54,750	-3,185	153,369

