	Primary endpoint of stroke (ischemic or hemorrhagic) and systemic embolism.	Measured 1 day after drug initiation in primary diagnosis position specified below and inpatient care setting: Stroke: ICD-9 discharge diagnosis codes: 430.xx Subarachnoid hemorrhage (SAH) 431.xx Intracerebral hemorrhage (ICH) 433.x1 Occlusion and stenosis of precerbral arteries with cerebral infarction 434.xx (excluding 434.x0) Occlusion and stenosis of cerebral arteries with cerebral infarction 436.x Acute, but ill-defined cerebrovascular events Systemic embolism: ICD-9 discharge diagnosis code: 444.xx Arterial embolism ICD-10 discharge diagnosis code: I74.x Arterial embolism and thrombosis	
For stroke: PPV of 85% or higher for ischemic stroke PPV ranging from 80% to 98% for hemorrhagic stroke →[Andrade SE, Harrold LR, Tjia J, et al. A systematic review of validated methods for identifying cerebrovascular accident or transient ischemic attack using administrative data. Pharmacoepidemiology and Drug Safety 2012;21 Suppl 1:100-28.] →[Tirschwell DL, Longstreth WT, Jr. Validating administrative data in stroke research. Stroke; a journal of cerebral circulation 2002;33:2465-70.] →[Roumali CL, Mitchell E, Gideon PS, Varas-Lorenzo C, Castellsague J, Griffin MR. Validation of ICD-9 codes with a high positive predictive value for incident strokes resulting in hospitalization using Medicaid health data. Pharmacoepidemiology and drug safety 2008;17:20-6.]
	Can't be measured in claims but not important for the analysis
		INCLUSION CRITERIA		
1	Men or women aged ≥18 years	Measured on the day of drug initiation: Age >=18		
2	Non-valvular Atrial fibrillation Atrial fibrillation must be documented by ECG evidence (e.g., 12-lead ECG, rhythm strip, Holter, pacemaker interrogation) within 30 days before randomization. In addition, subjects must have medical evidence of atrial fibrillation within 1 year before and at least one day before the qualifying ECG evidence. This could be obtained from a notation in the subject's record (e.g., medical chart, hospital discharge summary).	Measured 12 months prior to and including day of drug initiation, with >2 diagnoses separated by at least 14 days, in any diagnosis position and inpatient or outpatient care setting: Atrial fibrillation: ICD-9 diagnosis: 427.31 ICD-10 diagnosis: I48.0x, I48.1x, I48.2x, I48.9x		

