3	Non-valvular Atrial fibrillation Subjects with newly diagnosed atrial fibrillation are eligible provided that: - there is evidence that the atrial fibrillation is non-valvular - cardioversion is not planned - there is ECG evidence on 2 occasions 24 hours apart demonstrating atrial fibrillation			
	For Inclusion Criteria 4 It is either A) History of ischemic stroke or TIA or arterial embolism -OR- B) 2 of the following 4 1) Heart failure 2) Hypertension 3) Age >=75 4) Diabetes			
4	History of prior ischemic stroke, TIA or non-CNS systemic embolism believed to be cardioembolic in origin	Measured any time prior to and including day of drug initiation in any diagnosis position and inpatient or outpatient care setting: Ischemic stroke: ICD-9 diagnosis: 433.x, 434. x, 436.xx TIA: ICD-9 diagnosis: 435.xx Systemic embolism: ICD-9 diagnosis: 444.xx	
Patorno, Elisabetta et al. "Cardiovascular outcomes associated with canagliflozin versus other non-gliflozin antidiabetic drugs: population based cohort study." BMJ 2018;360:k119 http://dx.doi.org/10.1136/bmj.k119
 
Patorno, Elisabetta et al. "Empagliflozin and the Risk of Heart Failure Hospitalization in Routine Clinical Care: A First Analysis from the Empagliflozin Comparative Effectiveness and Safety (EMPRISE) Study." Circulation. 2019 Apr 8. doi: 10.1161/CIRCULATIONAHA.118.039177
	
	OR 2 or more of the following risk factors	Measured anytime prior to and including day of drug initiation in any diagnosis position and inpatient or outpatient care setting:		
4a	– Heart failure and/or left ventricular ejection fraction ≤35%	Heart failure: ICD-9 diagnosis: 428.x, 398.91, 402.01, 402.11, 402.91, 404.01, 404.11, 404.91, 404.03, 404.13, 404.93	
Patorno, Elisabetta et al. "Cardiovascular outcomes associated with canagliflozin versus other non-gliflozin antidiabetic drugs: population based cohort study." BMJ 2018;360:k119 http://dx.doi.org/10.1136/bmj.k119
 
Patorno, Elisabetta et al. "Empagliflozin and the Risk of Heart Failure Hospitalization in Routine Clinical Care: A First Analysis from the Empagliflozin Comparative Effectiveness and Safety (EMPRISE) Study." Circulation. 2019 Apr 8. doi: 10.1161/CIRCULATIONAHA.118.039177
	

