5	
Female subjects must be postmenopausal (for at least 2 years), surgically sterile, abstinent, or, if sexually active, be practicing an effective method of birth control (e.g., prescription oral contraceptives, contraceptive injections, intrauterine device, double-barrier method, contraceptive patch, male partner sterilization) before entry and throughout the study; and, for those of childbearing potential, have a negative serum β-hCG pregnancy test at screening.
	N/A	We will incorporate this by excluding 'pregnant' women below.
6	Subjects must have signed an informed consent document indicating that they understand the purpose of and procedures required for the study and are willing to participate in the study	N/A	
7	In order to participate in the optional pharmacogenomic component, subjects must have signed the informed consent for DNA research document indicating willingness to participate in the pharmacogenomics component of the study (where local regulations permit)	N/A	
EXCLUSION CRITERIA			
1	Cardiac-Related Conditions		
1a	Hemodynamically significant mitral valve stenosis	
Measured 180 days prior to and including day of drug initiation in any diagnosis position and inpatient or outpatient care setting:
 
Mitral stenosis: ICD-9 diagnosis: 396.0x, 396.1x ICD-10 diagnosis: I34.2x, I05.1x, I05.2x
	
1b	Prosthetic heart valve (annuloplasty with or without prosthetic ring, commissurotomy and/or valvuloplasty are permitted)	
Measured 180 days prior to and including day of drug initiation in any diagnosis position and inpatient or outpatient care setting:
 
ICD-9 diagnosis: V43.3x ICD-10 diagnosis: Z95.2x
 
CPT procedure: (TAVR with prosthetic valve) 33361, 33362, 33363, 33364, 33365, 33366, 33367, 33368, 33369, 33477, 0483T, 0484T, 0569T, 0570T
	
1c	Planned cardioversion (electrical or pharmacological)	N/A	Will not capture 'planned' procedures
1d	Transient atrial fibrillation caused by a reversible disorder (e.g., thyrotoxicosis, PE, recent surgery, MI)	N/A	Transient AF would not be well captured in claims.

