Appendix A

1f	Active endocarditis	
Measured 180 days prior to and including day of drug initiation in any diagnosis position and inpatient or outpatient care setting:
 
Endocarditis: ICD-9 diagnosis: 421.xx , 424.9x ICD-10 diagnosis: I33.xx, I38.xx, I39.xx
	
Tan, Charlie et al. "Accuracy of administrative data for identification of patients with infective endocarditis." International journal of cardiology vol. 224 (2016): 162-164. doi:10.1016/j.ijcard.2016.09.030

2	Hemorrhage Risk-Related Criteria		
2a	Active internal bleeding	
Measured 180 days prior to and including day of drug initiation in any diagnosis position and inpatient or outpatient care setting: Refer to the 'Bleeding' sheet for detailed codes (includes GI bleeding, intracranial, intra-articular bleeding mentioned in exclusion 2b)
	
2b	
History of or condition associated with increased bleeding risk including, but not limited to:
 
 - Major surgical procedure or trauma within 30 days before the randomization visit - Clinically significant gastrointestinal bleeding within 6 months before the randomization visit - History of intracranial, intraocular, spinal, or atraumatic intra-articular bleeding - Chronic hemorrhagic disorder - Known intracranial neoplasm, arteriovenous malformation, or aneurysm 	
Measured 30 days prior to and including day of drug initiation in diagnosis position and inpatient or outpatient care setting:
 
1) Major surgery: Major surgery selected from procedure codes range 40.x- 84.x -OR-
 
2) Hemorrhagic disorder (Bleeding diathesis) 286.x Coagulation defects 287.x Purpura and other hemorrhagic conditions -OR-
 
3) Intracranial neoplasm, AV malformation, aneurysm Intracranial neoplasm ICD-9 diagnosis: 225.xx ICD-10 diagnosis: D33.xx AV malformation ICD-9 diagnosis: 747.81 ICD-10 diagnosis: Q28.2x Cerebral aneurysm: ICD-9 diagnosis: 437.3x ICD-10 diagnosis: I67.1
	
2c	Planned invasive procedure with potential for uncontrolled bleeding, including major surgery	N/A	
2d	Platelet count <90,000/ μ L at the screening visit	
Measured 30 days prior to and including day of drug initiation in any diagnosis position and inpatient or outpatient care setting:
 
Thrombocytopenia: ICD-9 diagnosis: 287.3x, 287.4x, 287.5x
	

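### Exclusion 1a as printed omits ICD-9 394.0 and 394.2 and ICD-10 I05.0 and lists an insufficiency-only code, so some mitral stenosis stays in a nonvalvular AF cohort

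*Combined protocol and SAP*

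**What the plan says.** Section 1.2 sets the population: "To compare the risk of stroke or systemic embolism in nonvalvular atrial fibrillation (AF) patients at increased risk for stroke". Among the inclusion criteria in Appendix A, the trial's rule for newly diagnosed patients requires that "there is evidence that the atrial fibrillation is non-valvular".

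AF itself is identified by "ICD-9 diagnosis: 427.31 ICD-10 diagnosis: I48.0x, I48.1x, I48.2x, I48.9x". These codes do not separate valvular from nonvalvular AF, so the exclusions have to do that work.

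The trial criterion behind exclusion 1a is "Hemodynamically significant mitral valve stenosis". The claims version, labelled as mitral stenosis and measured over 180 days up to and including the index date, is "ICD-9 diagnosis: 396.0x, 396.1x ICD-10 diagnosis: I34.2x, I05.1x, I05.2x".

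The flowchart in section 5.3 reports the row "Excluded based on Exclusion #1a - Mitral stenosis" with 275 patients removed in Optum, 154 in Truven and 399 in Medicare.

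The header of Appendix A says that full ICD-10 lists are kept in an external folder because of file size. It also sends the reader there for anything missing.

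**The concern.** The ICD-10 line takes I05.1 and I05.2 but skips I05.0. The ICD-9 line starts in the 396 series and contains nothing from the 394 series. In the standard classification, the skipped codes include those for mitral stenosis on its own.

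If the criterion was run as printed, three things follow:

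- Some patients with native mitral stenosis remain in a cohort defined as nonvalvular.
- Some patients with mitral regurgitation alone are removed, although the criterion names stenosis.
- The definition of the lesion changes between the two coding systems.

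What is at stake is mainly fidelity to the trial population. There may also be some confounding. Section 5.2.1 notes that rivaroxaban was approved for nonvalvular AF, so retained patients could plausibly be concentrated among warfarin users.

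**Working it through.** **Code content.** The meanings below are those of the standard ICD classification, an input from outside the documents.

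| Code | Meaning | Stenosis? | Printed in 1a? |
|---|---|---|---|
| ICD-9 394.0 | mitral stenosis | yes | no |
| ICD-9 394.2 | mitral stenosis with insufficiency | yes | no |
| ICD-9 396.0, 396.1 | mitral stenosis combined with aortic valve disease | yes | yes |
| ICD-10 I05.0 | rheumatic mitral stenosis | yes | no |
| ICD-10 I05.1 | rheumatic mitral insufficiency | no | yes |
| ICD-10 I05.2 | rheumatic mitral stenosis with insufficiency | yes | yes |
| ICD-10 I34.2 | nonrheumatic mitral stenosis | yes | yes |

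The codes 394.0, 394.2 and I05.0 appear nowhere in the document. Cohort entry starts on November 4, 2011 (section 5.2.1), and the plan uses both coding systems, so the ICD-9 line applies to part of accrual.

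**Does another rule close the gap?**

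- Exclusion 1b lists "ICD-9 diagnosis: V43.3x ICD-10 diagnosis: Z95.2x" plus procedure codes. These are prosthetic valves.
- Exclusion 1e covers atrial myxoma and left ventricular thrombus.
- Exclusion 1f lists "ICD-9 diagnosis: 421.xx , 424.9x ICD-10 diagnosis: I33.xx, I38.xx, I39.xx". These are endocarditis codes, with nothing from 394 or I05.
- No row of Table 1 in Appendix B names mitral stenosis or valve disease. There is an Other CVD row, but its codes are not given.

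**Flowchart.** The printed subtraction reproduces exactly:

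- Optum: 56,644 − 275 = 56,369 (0.49% removed)
- Truven: 62,534 − 154 = 62,380 (0.25%)
- Medicare: 181,510 − 399 = 181,111 (0.22%)
- Total: 275 + 154 + 399 = 828 of 56,644 + 62,534 + 181,510 = 300,688, or 0.28%

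This counts whom the list caught. It says nothing about how many it missed.

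**Cost in power of correcting the list.** Formula: power = Φ(|ln HR| × √D / 2 − 1.96), with D the number of events.

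- The plan's own figure: D = 102,636 × 10.08 / 1,000 = 1,034.57. For HR 0.79, |ln HR| = 0.2357 and √D / 2 = 16.08, so power = Φ(1.83) = 0.966, as in section 10. For the margin 1.46, power is 0.99998, also as printed.
- Assume that 0.1% to 2% of patients carry only the missing codes. That is 224 to 4,478 of the final cohort of 40,604 + 50,085 + 133,230 = 223,919, or 103 to 2,053 of the 102,636 matched.
- At a 2% loss with events falling in proportion, D = 1,013.9. Superiority power is 0.964 and non-inferiority power stays above 0.9999.

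**Possible shift in the HR (illustration only).** Suppose retained stenosis has prevalence p_W in the warfarin arm and p_R in the rivaroxaban arm, and doubles the event risk. The HR is then multiplied by about (1 + p_R) / (1 + p_W). None of these inputs is in the documents. For assumed ranges p_W = 0.5% to 2% and p_R = 0.1% to 0.5%, the factor runs from 1.005 / 1.005 = 1.000 to 1.001 / 1.02 = 0.981. The shift is therefore between nothing and about 1.9% downward.

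**The case against.** The strongest reply is that the printed list may not be the implemented one. Appendix A keeps full ICD-10 lists in an external folder and points there for missing information in general. I05.0 may be on that list. This stands as a reason to check before concluding that the cohort is wrong. It does not clear the printed rule. Exclusion 1a prints explicit lists in both systems, the file-size explanation concerns ICD-10 only, and the ICD-9 line shows no sign of being partial.

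Second, the code meanings come from outside the document. That is true. However, the plan uses ICD as its working vocabulary, and the list cannot be read any other way.

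Third, codes do not grade severity, whereas the trial criterion concerns haemodynamically significant disease. This also stands: the number of retained patients who are truly ineligible is unknown, and a fuller list would remove some with mild stenosis. The same is true of the stenosis codes already printed.

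Two stronger readings are tempting and are not supported:

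- A reader might infer that isolated mitral stenosis passes exclusion 1a in both coding systems. In ICD-10 the gap is partial, because I34.2 and I05.2 are listed.
- A reader might infer that the propensity score cannot see the lesion at all. No row names it, but the content of Other CVD (38.4% and 38.0% after matching) is not given, and Table 1 includes possible correlates such as heart failure, loop diuretics and echocardiography. Adjustment can be neither shown nor ruled out.

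**Conclusion.** The concern holds for the rule as printed. The ICD-9 line misses mitral stenosis without aortic valve disease. The ICD-10 line misses I05.0 and takes a code for insufficiency alone. Nothing else among the exclusions makes up for this, so the printed rule does not deliver the nonvalvular population of section 1.2.

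Neither the number of patients affected nor the effect on the HR can be derived from the documents. The effect is probably small: the illustration spans 0% to about 1.9%, against a trial interval of 0.66 to 0.96. A reader might conclude that the omission flatters rivaroxaban. That direction follows only if retained patients were channelled to warfarin and carried a higher embolic risk, and the documents establish neither. No bias is shown from including I05.1, only unnecessary exclusion.

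The conclusion rests on the standard ICD meanings and on the printed list being the one that was run.

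**What to change.** 1. Compare the list implemented in the platform and the list in the external folder with the one printed in Appendix A.
2. Set exclusion 1a to ICD-9 394.0, 394.2, 396.0 and 396.1, and ICD-10 I05.0, I05.2 and I34.2. Remove I05.1. Print the same list in Appendix A.
3. Rerun the 1a row and the rows below it in section 5.3, then redo the matching, Appendix B and the section 10 power table. Do this before outcomes are opened; section 13 is still blank and undated.

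The cost is one edited code list, a rerun, and a refreshed review of balance and power. A small number of patients is lost, including some with mild stenosis, and some with regurgitation only are regained. The loss of power is negligible.

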After review of initial feasibility and power analyses, complete creation of the remaining covariates (see Table 1 below for list of covariates). Again, using the dummy outcome of a 90-day gap in database enrollment, complete a 1:1 PS-matched analysis. The PS should include the complete list of covariates (excluding laboratory values, which are missing in some patients).

- Provide plot of PS distributions stratified by treatment group.

Note- Please refer to **Appendix B**.

- Report covariate balance after matching.

Note- For Table 1, please refer to **Appendix B**.

- Report reasons for censoring by treatment group.

	Overall	Referent	Exposure
Dummy Outcome	0 (0.00%)	0 (0.00%)	0 (0.00%)
Death	1,879 (1.83%)	946 (1.84%)	933 (1.82%)
Start of an additional exposure	3,238 (3.15%)	1,642 (3.20%)	1,596 (3.11%)
End of index exposure	71,983 (70.13%)	36,022 (70.19%)	35,961 (70.07%)
Specified date reached (Dec 17/Dec 18/Dec 19)	6,822 (6.65%)	3,196 (6.23%)	3,626 (7.07%)
End of patient enrollment	5,237 (5.10%)	2,408 (4.69%)	2,829 (5.51%)
Switch to other NOACs (for censoring) + nursing home admission	13,477 (13.13%)	7,104 (13.84%)	6,373 (12.42%)

- Report follow-up time by treatment group.

Median Follow-Up Time (Days) [IQR]			
Patient Group	Optum	Truven	Medicare
Overall Patient Population	98 [38-209]	98 [44-236]	98 [38-206]
Referent	98 [38-190]	98 [44-192]	98 [38-188]
Exposure	98 [38-231]	119 [44-281]	98 [38-228]

- Report overall risk of the primary outcome.

	Optum	MarketScan	Medicare	Pooled
Risk per 1,000 patients	7.00	7.33	12.05	10.08

10. Final Power Assessment

Date conducted:

- Re-calculate power in the appropriate excel table, using the revised number of matched patients from the PS-match in Section 9. All other parameters in the table should be the same as in Section 8.

- For rivaroxaban vs. warfarin

- Pooled

Superiority Analysis		Non-inferiority Analysis	
Number of patients matched	102,636	Number of patients matched	102,636
Reference	51,318	Reference	51,318
Exposed	51,318	Exposed	51,318
Risk per 1,000 patients	10.08	Risk per 1,000 patients	10.08
Desired HR from RCT	0.79	Assumed HR from RCT	1
Alpha (2-sided)	0.05	Alpha (2-sided)	0.05
		Non-inferiority margin	1.46
Number of events expected	1034.57088	Number of events expected	1034.57088
Power	0.966450516	Power	0.999981559

o Optum

Superiority Analysis		Non-inferiority Analysis	
Number of patients matched	17,900	Number of patients matched	17,900
Reference	8,950	Reference	8,950

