Appendix A

#	ROCKET-AF trial definitions	Implementation in routine care	References/Rationale	Color coding
	Trial details- Primary indication, 4a- Unintended S with label change HR = 0.79 (95% CI 0.66-0.96)		
Please see the following Google Drive for further details or any missing information: https://drive.google.com/open?id=1WDb18wvwIIfakell7cuK-VCmb6b-gV
	Criteria
			
ICD-10 codes are not listed in this document because of excel file size limitations and excessive number of ICD-10 codes. Full ICD-10 code lists will be available in the above Google Drive Folder (link above). ICD-9 to ICD-10 code conversions were completed using a SAS macro that implements forward/ backward mapping based on the CMS ICD-9 to ICD-10 mapping: https://www.ncbi.nlm.nih.gov/pmc/articles/PMC3070730/
	Adequate mapping in claims
		EXPOSURE vs. COMPARISON		
	Rivaroxaban vs. Warfarin	Rivaroxaban 20mg OR 15mg daily (if low GFR) vs. adjusted-dose warfarin		Intermediate mapping in claims
		PRIMARY OUTCOME		Poor mapping or cannot be measured in claims

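### The printed prosthetic-valve exclusion (1b) has no surgical valve-replacement procedure codes, so some ineligible patients can stay in a cohort meant to be non-valvular

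*Combined protocol and SAP*

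**What the plan says.** The trial criterion in Appendix A, exclusion 1b, reads "Prosthetic heart valve (annuloplasty with or without prosthetic ring, commissurotomy and/or valvuloplasty are permitted". Its implementation in claims has three parts.

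- **Window and setting:** "Measured 180 days prior to and including day of drug initiation in any diagnosis position and inpatient or outpatient care setting".
- **Diagnosis codes:** "ICD-9 diagnosis: V43.3x ICD-10 diagnosis: Z95.2x".
- **Procedure codes:** 14 CPT codes under a single transcatheter label, starting "CPT procedure: (TAVR with prosthetic valve) 33361, 33362, 33363, 33364, 33365, 33366". No surgical valve-replacement group and no ICD procedure code is printed.

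One other rule could catch a recent operation. Exclusion 2b uses a 30-day window and "Major surgery selected from procedure codes range 40.x- 84.x".

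The head of Appendix A adds a caveat: "ICD-10 codes are not listed in this document because of excel file size limitations and excessive number of ICD-10 codes". It points to an external folder for the full ICD-10 lists.

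The flowchart in Section 5.3, in the row "Excluded based on Exclusion #1b - Prosthetic heart valve", shows 1,238 patients removed in Optum, 789 in Truven and 3,016 in Medicare. The counts are not split by arm or by code.

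**The concern.** Section 1.2 defines the target population as nonvalvular atrial fibrillation. The inclusion rows for atrial fibrillation (2 and 3) are implemented with arrhythmia codes only, so non-valvular status rests mainly on exclusions 1a and 1b. For transcatheter valves the authors did not rely on a diagnosis record alone; they added procedure codes. The same reasoning applies to surgical replacement, and there they list none.

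Run as printed, the rule can retain patients whom the emulated trial would have excluded. If those patients have a different outcome risk and are unevenly spread between arms, the hazard ratio shifts. Appendix B names no valve-replacement covariate. Its named cardiac-procedure variables are coronary (CABG, PTCA, stent), so no balance row would show such an imbalance directly.

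**Working it through.** **1. Who is caught and who is not.** Take a patient with a surgically implanted valve.

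- V43.3x or Z95.2x recorded in the 180 days: excluded by 1b. As printed, neither family is limited to transcatheter valves.
- Neither recorded: the only other route in 1b is a CPT code, and all 14 carry the transcatheter label. The patient stays in.
- Exclusion 2b: covers 30 days, not 180. Its codes are selected from 40.x-84.x, and the selected list is not printed. Valve surgery is not named. Appendix A itself cites vascular ICD-9 procedure codes below 40 (39.95, hemodialysis), so the range cannot be taken to cover cardiovascular procedures.
- The caveat on unprinted lists concerns ICD-10. It does not account for missing CPT or ICD-9 procedure codes.

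**2. Reproducing the attrition row (Section 5.3).**

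- Optum: 56,369 - 1,238 = 55,131 (2.20% removed)
- Truven: 62,380 - 789 = 61,591 (1.26%)
- Medicare: 181,111 - 3,016 = 178,095 (1.67%)
- Total removed: 5,043 of 299,860 = 1.68%, leaving 294,817

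All three agree with the flowchart.

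**3. Illustrative size.** The documents give no count of missed patients, so the following are assumptions: 10-25% as many again are missed; all are on warfarin and none on rivaroxaban; they have m = 3 times the outcome rate; later exclusions and matching remove them in proportion.

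- Missed at step 1b: 0.10 × 5,043 = 504 to 0.25 × 5,043 = 1,261
- Fraction surviving later exclusions: final cohort 40,604 + 50,085 + 133,230 = 223,919; 223,919 / 294,817 = 0.76
- Remaining: about 380 to 960
- Share s of the 150,399 unmatched warfarin patients (Appendix B): 0.25% to 0.64%
- Observed HR = true HR / (1 + s(m - 1))
- True HR 1.00: 1/1.0051 = 0.995 to 1/1.0127 = 0.987
- True HR 0.79: 0.786 to 0.780

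Sensitivity of a true HR of 1.00 to the assumed share and risk:

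| s | m = 0.5 | m = 2 | m = 3 |
|---|---|---|---|
| 0.5% | 1.003 | 0.995 | 0.990 |
| 1% | 1.005 | 0.990 | 0.980 |
| 2% | 1.010 | 0.980 | 0.962 |

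The bottom row is extreme. 2% of 150,399 is 3,008 patients, or 3,008 / 0.76 = about 3,960 at step 1b. That is nearly 80% as many as the rule already removes, all in one arm.

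**4. Against the study's precision.** Section 10 expects 1,034.57 pooled events. With 1:1 matching, SE(log HR) is about 2/√1,034.57 = 0.062. The shifts in step 3 are ln(1.0051) = 0.005 and ln(1.0127) = 0.013, or about 0.1 to 0.2 SE.

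**5. Power after a wider exclusion.** The pooled superiority power of 0.966 in Section 10 reproduces with the Schoenfeld formula. Dropping 0.5% to 3% of matched pairs leaves 0.966 to 0.962.

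**The case against.** The strongest reply is that the gap is conditional. The two diagnosis families apply in any position and in inpatient or outpatient care over 180 days, so surgical recipients are removed whenever either is recorded. Some or many of the 5,043 may be surgical, and nothing printed shows that any were missed. This stands, and it limits the point to recipients with no such record in the window.

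Three stronger readings are tempting, and the documents do not support them.

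- **That the retained patients are mostly on warfarin, so the result favours rivaroxaban.** This is plausible, but no 1b count is split by arm and Appendix B has no valve variable. After matching, the prior coronary-procedure variable is higher on warfarin (864, 1.7%, against 550, 1.1%). That shows a single component can stay uneven when the score uses a combined variable; it does not locate valve recipients.
- **That the propensity score cannot balance them.** Correlates of recent cardiac surgery are in the tables and close after matching: hospitalization in the prior 30 days (29.7% v 29.3%), heparin use (4.3% v 0.4% before, 0.4% v 0.6% after) and mean INR tests (3.13 v 0.33 before, 0.41 v 0.39 after). These are partial proxies and do not prove balance, but they rule out saying that it cannot be achieved.
- **That tissue-valve status codes were left out.** What V43.3x and Z95.2x cover is a matter of coding definitions that the documents do not give, and the full ICD-10 lists are held elsewhere. For ICD-10, absence from print does not establish absence from the implementation.

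Appendix A also has a colour key for mapping quality that did not survive in the text, so the authors may already have marked 1b as imperfectly mapped.

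**Conclusion.** The point holds as a gap in the printed eligibility rule. The criterion covers any prosthetic valve, the printed procedure codes cover transcatheter valves only, and no other printed rule or named covariate clearly catches a surgical recipient without a diagnosis record in the 180 days. The number of such patients, their arm and the direction of any bias are unknown.

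On assumptions that place all of them on warfarin at three times the risk, a true hazard ratio of 1.00 reads about 0.987 to 0.995. A lower risk in the missed group would move it the other way. A shift of this size does not materially affect the comparison with the 1.46 margin or the power. This is a small correction to cohort eligibility and not a threat to the study's conclusion. It is worth making because it is specific and cheap, and because Section 13 records no comparative analysis, so it can still be made without reference to outcome results.

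**What to change.** In exclusion 1b:

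- Add surgical valve-replacement procedure codes in CPT, ICD-9 procedure and ICD-10-PCS.
- Check the full code list for tissue-valve status codes (V42.2, Z95.3, Z95.4; definitions to be confirmed against the coding manuals) and add any that are absent.
- Keep repair codes out, since the criterion permits repair.

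Print the complete 1b list in Appendix A. Re-run the cohort and the matching before the comparative analysis, and report by arm and database how many further patients are removed. That count replaces the assumptions used above. The cost is a code-list edit, a cohort re-run and slightly fewer patients.
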